**[name]**

# 1. BACKGROUND AND RATIONALE

Diabetes mellitus (DM) is a chronic metabolic disorder characterized by hyperglycemia, resulting from deficient insulin secretion, reduced insulin action, or both. According to the 11th edition of the International Diabetes Federation (IDF) Diabetes Atlas (2025), approximately 589 million adults worldwide are living with diabetes, and this number is projected to reach 853 million by 2050 (IDF, 2025). In Turkey, the prevalence of diabetes has increased from 7.2% (TURDEP-I, 1997-1998) to 13.7% (TURDEP-II, 2010), placing the country among the highest-prevalence nations in the European region. As of 2024, approximately 7.5 million adults aged 20-79 in Turkey are estimated to have diabetes (IDF, 2025; American Diabetes Association Professional Practice Committee, 2024).

Diabetic foot ulcer (DFU) is one of the most serious and burdensome complications of diabetes. The lifetime risk of developing a foot ulcer in individuals with diabetes is 19-34%, and approximately 20% of these lesions may result in lower extremity amputation (Armstrong et al., 2023). A multicenter study conducted in Turkey found active DFU in 17.1% of adult patients with diabetes, underscoring the national significance of this problem (Armstrong et al., 2023).

Diabetic foot care is a complex nursing procedure that involves wound assessment, infection control, appropriate dressing application, and patient education (Armstrong et al., 2023). During this process, patients frequently experience significant procedure-related pain and anxiety, which can impair adherence to care, trigger stress-related changes in vital signs (pulse rate, respiratory rate, blood pressure), and prolong healing. Therefore, simultaneous management of pain, anxiety, and vital sign stability is considered an important component of nursing practice in diabetic foot care.

In recent years, growing interest in non-pharmacological approaches for pain and anxiety management has led to the investigation of virtual reality (VR) as a distraction-based intervention. VR immerses the individual in an interactive three-dimensional digital environment, cognitively distracting them from nociceptive stimuli. This mechanism is supported by the Gate Control Theory (Melzack & Wall, 1965), which posits that competitive sensory input can suppress pain signal transmission to the central nervous system. Evidence from pediatric and adult settings has demonstrated that VR reduces pain and anxiety during invasive procedures such as wound care, vascular access, vaccination, and post-operative recovery, and may exert stabilizing effects on heart rate, blood pressure, respiratory rate, and oxygen saturation (Zeng et al., 2019; Baidhowy et al., 2024).

Despite promising evidence in other clinical settings, studies specifically addressing VR during diabetic foot care are limited (Baidhowy et al., 2024). The present study was therefore designed to rigorously evaluate the effect of a VR intervention on pain, state anxiety, and vital signs in patients with diabetic foot ulcers undergoing wound care in a hospital setting.

## 2. STUDY OBJECTIVES AND HYPOTHESES

### 2.1 Primary Objective

To determine the effect of virtual reality (VR) application during foot care on the pain level, state anxiety, and vital signs (body temperature, oxygen saturation, pulse rate, respiratory rate, systolic and diastolic blood pressure) of individuals with diabetic foot ulcers.

### 2.2 Study Hypotheses

H1: Virtual reality application during foot care has an effect on pain level in individuals with diabetic foot ulcers.

H12: Virtual reality application during foot care has an effect on state anxiety in individuals with diabetic foot ulcers.

H13: Virtual reality application during foot care has an effect on vital signs in individuals with diabetic foot ulcers.

### **3. STUDY DESIGN**

This study is a single-center, randomized controlled experimental trial with a pre-test/post-test design, conducted at Malatya Turgut Ozal University Training and Research Hospital (Orthopedics Unit and Chronic Wound Care Unit), Malatya, Turkey.

Study Period: December 9, 2024 - June 15, 2025

Study Design: Randomized Controlled Trial (RCT)

Blinding: Single-blind (outcome assessor blind to group allocation)

Allocation: Random (computer-generated block randomization list)

### **4. STUDY POPULATION**

#### **4.1 Target Population**

Adult individuals with diabetes mellitus who were receiving diabetic foot wound care at the Orthopedics Unit and Chronic Wound Care Unit of Malatya Turgut Ozal University Training and Research Hospital, Malatya, Turkey.

#### **4.2 Inclusion Criteria**

- Age  $\geq$  18 years
- Confirmed diagnosis of Type 2 Diabetes Mellitus
- Presence of a diabetic foot ulcer classified as Grade 3 or Grade 4 according to the Wagner Classification System (Wagner, 1981)
- Ability to communicate verbally
- Able to read and write Turkish
- Willingness to participate in the study and provide written informed consent

#### **4.3 Exclusion Criteria**

- Presence of a chronic wound other than diabetic foot (e.g., arterial or venous ulcer)
- Age  $<$  18 years
- Cognitive impairment or altered level of consciousness precluding completion of study measures
- Inability to use VR goggles (e.g., severe visual or vestibular disorder)

#### **4.4 Sample Size**

The sample size was calculated using G\*Power 3.1 software. In the absence of studies specifically examining VR in diabetic foot patients, the effect size ( $d = 0.46$ ) was derived from a meta-analysis by Zeng et al. (2019) on VR effects on anxiety and pain. With  $\alpha = 0.05$  and power = 0.95, the required sample was 64 participants (32 per group). Accounting for approximately 5% possible attrition, 68 participants were randomized. Analyses were performed on the 64 participants who completed the study.

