### **8.3 Within-Group Pre-Post Comparisons**

Paired samples t-test was used to compare pre-test and post-test scores within each group (intervention and control) for all outcome variables.

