### **8.4 Between-Group Comparisons of Change Scores**

Independent samples t-test was used to compare the magnitude of change (post-test minus pre-test) between the intervention and control groups for each outcome variable.

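### Section 4.4 claims power 0.95 with 32 per group at d = 0.46, but the planned between-group t-test does not have that power: it has 44% (two-sided) if d is in change-score SDs

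*Combined protocol and SAP*

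**What the plan says.** Section 4.4 (Sample Size) reports a G*Power calculation. The effect size, d = 0.46, is taken from a meta-analysis of VR for anxiety and pain. With alpha = 0.05 and "power = 0.95, the required sample was 64 participants (32 per group"). It then adds: "Accounting for approximately 5% possible attrition, 68 participants were randomized". The 64 completers were analysed. The section does not name the test behind the calculation, its sidedness, the SD that d refers to, or any pre-post correlation.

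Section 8.4 gives the only between-group test of the outcomes: "Independent samples t-test was used to compare the magnitude of change (post-test minus pre-test) between the intervention and control groups for each outcome variable". Section 8.3 adds tests inside each arm: "Paired samples t-test was used to compare pre-test and post-test scores within each group". Section 7.1 names two primary outcomes, VAS pain and STAI-I state anxiety. The hypotheses in Section 2.2 are non-directional, for example "Virtual reality application during foot care has an effect on pain level in individuals with diabetic foot ulcers". Section 8.5 plans Cohen's d for between-group differences. Section 8 plans no confidence intervals.

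**The concern.** A standardised difference of 0.46 is modest, and a two-arm comparison needs well over 32 per arm to detect it with 95% power. The stated inputs and the stated sample size therefore do not fit the test in Section 8.4.

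The power statement tells a reader how to take a non-significant pain or anxiety result. A stated power of 0.95 implies a 5% chance of missing the planned effect. If the true chance is much larger, a non-significant result carries far less weight against that effect than Section 4.4 suggests.

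**Working it through.** **Inputs.** d = 0.46, alpha = 0.05, stated power 0.95, 32 per group analysed, 68 randomised (all Section 4.4). Independent t-test on change scores (Section 8.4). Sidedness is not stated; two-sided is assumed because the hypotheses are non-directional, and one-sided is shown as well.

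**Step 1: the stated figure, using the planned test.** With n per group, df = 2n − 2 and the noncentrality is d × √(n/2). For n = 32, df = 62 and the noncentrality is 0.46 × √16 = 1.84. Exact power from the noncentral t distribution, with d in SDs of the analysed change score:

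| | Two-sided | One-sided |
|---|---|---|
| Power, 32 per group | 44.1% | 56.9% |
| Power, 34 per group (all 68) | 46.4% | 59.2% |
| n per group for 0.95 | 124 (248 total) | 103 (206 total) |
| n per group for 0.80 | 76 (152 total) | 60 (120 total) |

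The stated 32 per group is not reproduced.

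**Step 2: calculations that do give 64.** Three were found, each with power 0.952. All have noncentrality 3.68 (3.68² = 13.54), which is twice the 1.84 of the planned test.

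- *Paired or one-sample t-test on 64 pairs, standardised change 0.46:* 0.46 × √64 = 3.68. The plan has 32 pairs in each arm, where two-sided paired power is 71.3%, and a within-arm test does not compare the arms.
- *Two-group ANOVA with 0.46 entered as Cohen's f:* f² × N = 0.2116 × 64 = 13.54. For two equal groups d = 2f, so this is d = 0.92.
- *Repeated-measures group-by-time interaction, f = 0.23, two time points, r = 0.5:* f² × N × 2 / (1 − r) = 0.0529 × 64 × 2 / 0.5 = 13.54. Here the difference in change is 4 × 0.23 = 0.92 raw SDs. The SD of change is √(2 × 0.5) = 1 raw SD, so this is again 0.92 SD.

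None of these is d = 0.46 in a comparison of two arms of 32.

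**Step 3: if d is in raw-score SDs.** The change score has SD √(2(1 − r)) raw SDs, so the effect on the analysed scale is 0.46 / √(2(1 − r)). The documents do not give r, so a range is shown (32 per group, two-sided):

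| r | Effect in change-score SDs | Power |
|---|---|---|
| 0.3 | 0.39 | 33% |
| 0.5 | 0.46 | 44% |
| 0.7 | 0.59 | 65% |
| 0.8 | 0.73 | 82% |
| 0.874 | 0.92 | 95% |

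The last row solves 0.46 / √(2(1 − r)) = 0.9155, the d that 32 per group detect with 95% power: r = 1 − (0.46/0.9155)²/2 = 0.874. One-sided, the detectable d is 0.8316 and the same formula gives r = 0.847.

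**Step 4: what 32 per group can show.** Two-sided, the detectable d is 0.71 at 80% power and 0.92 at 95% power. The 95% confidence interval for the difference has half-width t(0.975, 62) × √(2/32) = 0.50 change-score SDs. An observed difference of zero gives about −0.50 to 0.50. This includes 0.46 but excludes larger effects.

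**Step 5: attrition.** 64 / 0.95 = 67.4, rounded up to 68. This step is consistent.

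**The case against.** The strongest case on the other side is that Section 4.4 does not say which calculation was run. Section 3 describes a randomised pre-test/post-test design, so a repeated-measures interaction is a natural choice, and one with f = 0.23 and r = 0.5 returns exactly 64. If a high correlation was assumed and d was meant in raw-score SDs, power could be well above 44%. The two measurements lie on either side of a single foot-care session, so a high correlation cannot be ruled out.

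Part of this stands. The 44% is conditional, and the origin of 64 is unknown. A reader might infer that a particular slip was made in G*Power; the documents do not show one. A reader might also take the miss risk to be 56% (100 − 44) without qualification. That holds only for a two-sided test with d in change-score SDs, or with r = 0.5; over r from 0.3 to 0.8 the miss risk runs from 67% to 18%. None of this supports 0.95 as written. The interaction route corresponds to 0.92 SD, a one-sided test gives 57% with d in change-score SDs, and the raw-SD route needs a correlation that the plan never states.

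Two further readings go too far. One is that a null result would be uninformative: with a half-width of 0.50 SD, an estimate of zero still excludes larger effects. The other is that every non-significant result is inconclusive. The interval decides this: an estimate below 0.46 − 0.50 = −0.04 SD, taking benefit as positive, would exclude 0.46. Nor does low power bias the estimate or inflate the type I error. The documents also do not say that a non-significant result would be read as proof of no effect.

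**Conclusion.** The concern holds. The 0.95 claim is unsupported for the test in Section 8.4: 32 per group is about a quarter of the 124 that d = 0.46 requires two-sided when d is in change-score SDs. Under that scaling, power is 44% two-sided or 57% one-sided. Under raw-score scaling, it depends on the unstated correlation, as tabulated, and two-sided it reaches 95% only at about 0.87. The figures assume equal arms of 32, alpha 0.05 and the t-test model. The error affects the power statement and the reading of non-significant primary results; it does not invalidate the between-group test itself.

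**What to change.** Add a dated correction to Section 4.4. Keep the existing statement visible as the recorded basis of the sample size. State which G*Power test was run, its sidedness, the SD that d refers to, and any correlation assumed. Replace the 0.95 claim with:

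> 64 analysed participants (32 per group) give 44% power for d = 0.46 in change-score SD units (two-sided alpha 0.05, independent t-test), 80% power for d = 0.71 and 95% power for d = 0.92.

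If d was meant in raw-score SDs, add the range of power over r from Step 3. Label the correction as made after the sample size was set and derived from design inputs only.

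In Section 8.4 and the report, give the between-group mean difference with its 95% confidence interval (half-width about 0.50 change-score SDs) for VAS pain and STAI-I. Describe a non-significant result as inconclusive for the planned effect when the interval includes d = 0.46.

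The study period in Section 3 ended on June 15, 2025, and no extra enrolment is proposed. The cost is a few sentences and a less favourable stated power.

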## **5. RANDOMIZATION AND BLINDING**

### **5.1 Randomization**

Eligible participants were randomized to the intervention or control group using a computer-generated random selection method. Randomization was performed individually for each participant immediately after completion of pre-test measurements and prior to the onset of foot care. This approach minimized selection bias.

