### **7.4 Data Collection Procedure**

Data were collected at two time points using a face-to-face interview technique by the principal investigator:

Pre-test: Approximately 5 minutes before the start of foot care (after a minimum 5-minute rest period in the seated position). The Vital Signs Form, STAI-I, and VAS were administered. Participants were then randomized.

Post-test: Immediately after completion of foot care (within 0-2 minutes). The Vital Signs Form, STAI-I, and VAS were re-administered.

To ensure measurement standardization, all measurements were performed by the same researcher using the same equipment with participants in the same position. For blood pressure measurements, patients had rested for  $\geq 5$  minutes in a seated position and had abstained from caffeine for  $\geq 1$  hour and smoking for  $\geq 15$  minutes prior to measurement.

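### Only the 64 completers of 68 randomised are analysed, with no as-randomised or sensitivity analysis, so bias of unknown direction from the four losses cannot be excluded

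*Combined protocol and SAP*

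**What the plan says.** Section 4.4 (Sample Size) sets a requirement of 64, or 32 per group. It then enlarges the trial, "Accounting for approximately 5% possible attrition", so that "68 participants were randomized". The analysis set follows: "Analyses were performed on the 64 participants who completed the study". The term for completing the study is not defined.

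The order of events is in sections 5.1 and 7.4. Section 5.1 places randomisation "immediately after completion of pre-test measurements and prior to the onset of foot care". Section 7.4 agrees for the baseline measures: "The Vital Signs Form, STAI-I, and VAS were administered. Participants were then randomized". The second measurement is close behind: "Post-test: Immediately after completion of foot care (within 0-2 minutes"). Section 5.2 says that participants were not blinded.

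Section 8 compares change scores (post minus pre) between groups by an independent-samples t-test (8.4), which needs an observed post-test. Nowhere does section 8 define an as-randomised analysis set, a method for missing post-tests or a sensitivity analysis. The documents do not give the arm of any of the four losses or the reason for it.

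**The concern.** Randomisation protects the comparison only for the groups as randomised. Once people leave after allocation, the remaining groups are comparable only if leaving is unrelated to arm and outcome.

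This is a one-session trial, so the usual harmless causes of long-term attrition, such as moving away or missing a later visit, have little room to operate. Between randomisation and the post-test there is only an allocation known to the participant and one foot-care procedure, with or without a headset. A loss in that interval is possibly connected with the arm, with the pain or anxiety being measured, or with both.

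Both primary outcomes, pain and state anxiety (section 7.1), rest on the same 64 people. Without arms, reasons or a sensitivity analysis, a reader cannot tell whether the four losses matter.

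**Working it through.** **Inputs.** 68 randomised, 64 analysed, attrition of about 5%, d = 0.46 and α = 0.05 (section 4.4); VAS range 0 to 10 cm and STAI-I range 20 to 80 (section 7.1). *Assumptions:* 34 randomised per arm, because the actual split is not given, and a two-sided test, because sidedness is not stated.

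**Step 1: the plan's own figure.** Dividing by the retention rate gives 64/0.95 = 67.4, rounded up to 68. Multiplying gives 64 × 1.05 = 67.2, also rounded up to 68. The stated 68 reproduces.

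**Step 2: the loss.** 68 − 64 = 4, and 4/68 = 5.9%.

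**Step 3: how far the contrast could move.** If m of the n people in an arm are lost and their mean outcome differs from that of the arm's completers by k SD, the full-arm mean differs from the completer mean by (m/n) × k. The shift in the contrast is the VR term minus the control term.

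| Scenario (34 per arm) | k = 0.5 | k = 1 | k = 2 |
|---|---|---|---|
| All four in one arm: 4/34 × k | 0.06 SD | 0.12 SD | 0.24 SD |
| Two informative losses in one arm: 2/34 × k | 0.03 SD | 0.06 SD | 0.12 SD |
| Two per arm, same k in both: 2/34 × k − 2/34 × k | 0 | 0 | 0 |
| Uninformative losses (true difference zero) | 0 | 0 | 0 |

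Two losses per arm that depart in opposite directions give the same shift as the first row, because 2/34 × k + 2/34 × k = 4/34 × k.

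Against the planned d = 0.46, the first row is 0.059/0.46 = 13%, 0.118/0.46 = 26% and 0.235/0.46 = 51%. These percentages treat k and d as measured in the same SD, which section 4.4 does not specify. Every shift can have either sign. VR losses who did worse than VR completers mean that the completer analysis flatters VR. Control losses who did worse than control completers mean that it works against VR.

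**Step 4: no assumption about the missing values.** Each missing post-test could lie anywhere on its scale.
- VAS: 4/34 × 10 = 1.18 cm.
- STAI-I: 4/34 × (80 − 20) = 4/34 × 60 = 7.1 points.

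These are the widths over which the mean difference for all 68 is undetermined. With 34 per arm they do not depend on how the four losses split.

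**Step 5: a different split.** If 32 completed in each arm and all four losses came from one arm of 36, the shift for k = 1 to 2 is 4/36 × (1 to 2) = 0.11 to 0.22 SD. The widths are 4/36 × 10 = 1.11 cm and 4/36 × 60 = 6.7 points. The picture is unchanged.

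**Step 6: power.** By the exact noncentral t, a two-sided two-group test at d = 0.46 has power 44.1% with 32 per arm and 46.4% with 34 per arm. Having all 68 outcomes would gain very little power. The reason to change the analysis set is bias. (That these values are far from the planned 0.95 is a separate matter.)

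**The case against.** A reader might infer more than the documents say: that the four stopped because of the headset or the pain, that people who removed the headset were excluded, and that the result is therefore biased towards VR. None of this is supported.

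- No arm or reason is given for any loss. Section 9 allows withdrawal at any time, and there is an interval between randomisation and the start of care. An incomplete form or a missed post-test window would also produce a non-completer.
- Because completion is undefined, someone who took the headset off and still gave a post-test may be among the 64, in the assigned arm. The 64 may simply be everyone with an outcome.
- Section 4.3 excludes people unable to use the goggles, and section 6.1 says that the content was piloted for motion sickness. Both reduce the chance of headset intolerance, though neither removes it.
- Control participants who left because of pain would bias the comparison against VR. Similar losses in both arms would largely cancel.
- The largest shift needs all four losses in one arm, or opposite departures in the two arms. The only per-arm figure, 32 required per group, fits two losses per arm at least as well.
- Imputation from arm and pre-test assumes missing at random. With four missing values it would give nearly what a baseline-adjusted completer analysis gives, and it cannot correct for dropout driven by unobserved events during care.

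All of this stands, and it limits the point to a possible bias of unknown sign. It does not dispose of it. The planned attrition of about 5% justifies randomising 68, but not an analysis of completers alone. The same silence on arms and reasons that prevents a claim of bias also prevents a claim that there is none.

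**Conclusion.** The plan analyses completers only and offers nothing to show whether that matters. The four losses (5.9%) occurred after allocation, in a single session, among participants who knew their arm, so a link with arm and outcome is possible but not shown.

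On the assumption of 34 per arm, the illustrative shift ranges from about zero to 0.12 to 0.24 SD in either direction. Its upper part, 26% to 51% of the planned effect, is a worst case under stated assumptions and not an estimate. The assumption-free widths of about 1.2 cm on the VAS and 7 points on STAI-I bound what the four missing outcomes could do. A conclusion that VR is favoured by the exclusions, or that the dropout was caused by treatment, would go beyond the documents.

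This should be fixed: it is a gap in the analysis set, in reporting and in sensitivity analysis for both primary outcomes. It does not by itself invalidate the trial.

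**What to change.** 1. Define the primary analysis set as all 68 randomised participants in their assigned arm, whether or not the headset was kept on, and include every post-test obtained. Define what completing the study means.
2. For post-tests that are truly missing, use a baseline-adjusted likelihood model for pre-test and post-test, or multiple imputation from arm and pre-test. State that either assumes missing at random. Given the order of events in sections 5.1 and 7.4, all 68 pre-tests should exist.
3. Add a best/worst-case or delta-adjusted sensitivity analysis, in both directions and in both arms. This step, rather than the imputation, addresses losses related to unobserved outcomes.
4. Report the number randomised and lost in each arm, with the reason for each loss.
5. Keep the analysis of the 64 completers as supportive.

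The cost is revised wording in sections 4.4 and 8 and a few hours of analysis, with no new data collection. The gain in power is negligible (44.1% to 46.4% even if all 68 outcomes were available). The conclusion may become less firm once the sensitivity range is shown.
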